### **Methods and Timing for Assessing, Recording, and Analyzing Safety Parameters**

#### **Notification of Unplanned Healthcare Utilizations and Deaths**

Unplanned healthcare utilization (intensive care unit transfers, emergency department visits and/or hospitalizations) and deaths are monitored throughout all study phases for each Veteran. The study coordinator and research assistant share a study patient panel in the electronic health record. Any time a participant is admitted to the Nashville VA Medical Center, they are alerted. To identify if a Veteran experience an unplanned healthcare utilization at an outside hospital (OSH), the Veterans are asked at each follow-up time point if they have been to an emergency room or had an inpatient stay, and if so, at what facility. Additionally, the research assistant or study clinician reviews VISTA for any uploaded OSH records at the time of the follow-up calls. The research assistant is responsible for requesting medical records from OSHs (and SNFs) relevant to the utilization.

### **Review of Unplanned Healthcare Utilizations and Deaths**

Any unplanned healthcare utilization or unexpected death (e.g., patient not receiving hospice care) is reviewed to determine if it was an adverse event that was serious, related to the study, and unexpected (SUSAR). Once all necessary records have been obtained by the research assistant, the case is assigned to a physician co-investigator (adjudicator) blinded to group assignment. Through a structured review protocol of all relevant medical records from both within and outside of VA, the adjudicator uses an established methodology to determine the presence of serious medication errors. Clinician-adjudicators will decide whether the unplanned healthcare utilization is related to medication withdrawal (i.e., ADWE) using the 10-question Drug Withdrawal Probability Scale, a scale based on the Naranjo algorithm, which is a validated scoring system to assess causality of adverse drug events. ADWE will be coded as definite (>8), probable (5-8), possible (1-4), and doubtful (<1). For all ADWEs, clinician-adjudicators will then determine whether it was avoidable by any change in management.

After review by the clinician-adjudicator, the case is sent to the Principal Investigator to review to determine if the event was unexpected and/or study related. Should the event be determined as SUSAR (serious, unexpected, and study related) it will be reported as such to the DSMB and IRB as outlined below.

### **Adverse Event Reporting Procedures**

The Principal Investigators (PIs) are responsible for reporting to the respective governing bodies in accordance with their prescribed timelines and regulations.

### **Institutional Review Board**

PIs will notify the IRB of any Serious, Unexpected, Study Related Adverse Event within 7 days of PI notification of the event. All deaths regardless of study relatedness will be reported to the IRB within 7 days of PI notification. At the time of the IRB annual continuing review, the IRB will receive (1) a listing of all adverse events, and (2) copies of the reports generated from DSMB meetings. If the DSMB meeting report identifies a new risk to or a change in the risk benefit ratio, the IRB will be notified within 5 days of PIs receipt of the report.

### **Data Safety Monitoring Board (DSMB)**

The Health Services Research and Development Service (HSR&D) Data and Safety Monitoring Board convenes annually in March. The PI will submit a report to the VA Program Officer and DSMB coordinator by January 31st each year. This report will include case listings for all deaths, serious adverse events, and non-serious adverse events regardless of unexpectedness or study relatedness. At the conclusion of the closed session meeting, the DSMB will note any concerns about Veteran safety and issue an approval for study continuation. In the event that the DSMB has additional concerns, issues a conditional approval, or requests a temporary study stoppage, the PIs will be given 30 days to respond to the DSMBs concerns.

## **STATISTICAL CONSIDERATIONS**

### **Sample Size and Randomization**

Existing data indicate that approximately 600 to 700 hospitalized Veterans are referred to SNF annually. Thus, we conservatively estimate that 40% (or, 240 per year) will provide consent, complete baseline assessments and discharge to SNF to yield a total consented sample of 540 across all study months. During the SNF stay, we anticipate ~5% will die, which will leave 513 (or ~256 per group) discharged from SNF. Based on preliminary data, ~15% of patients die within 90 days of SNF discharge. Thus, ~85% (or 393 total) will be alive at 90 days. In addition, we estimate we will be unable to reach ~10%, which will leave ~354 total participants (~177/group) for 90-day follow-up. The population and sample size were adjusted mid-study due to the significant enrollment and retention challenges caused by the COVID-19 pandemic.

It was determined that a sample of 260 Veterans was sufficient to provide power greater than 93% for both the primary and secondary outcomes. Finally, the study enrollment was continued for an additional 10 months beyond the original project timeline.

Participants will be randomized in a 1:1 ratio using permuted blocks of two or four, where the size for each block is selected uniformly at random. This type of randomization ensures balance across the intervention and control groups after every second or fourth randomization (depending on the size of the current block). This randomization scheme will be generated by computer using the Mersenne-Twister pseudo random number.

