There is a dearth of evidence related to the management of multiple co-existing geriatric syndromes, and few interventions have been implemented to reduce medications while also monitoring health outcomes. The relationship between polypharmacy, adverse drug events and geriatric syndromes in the VA population supports the rationale for an intervention focused on deprescribing medications before hospital discharge. We have pilot-tested a multifaceted intervention (Drug Reduction in Older Patients, DROP) to engage patients and providers to reduce the number and/or dose of medications prior to hospital discharge. The proposed randomized, controlled trial is powered to evaluate the effect of this intervention on a reduction in medications as defined by the total number of prescribed medications, the number of PIMs, anticholinergic and sedative drug burden and the number of medications associated with geriatric syndromes. In addition, we will collect relevant data on the prevalence and severity of geriatric syndromes and other clinical outcomes. We also will use a hybrid research design to evaluate both effectiveness and implementation issues to better inform future adoption and sustainability. Our overarching hypothesis is that a hospital-based intervention to safely reduce the total number of medications represents the most feasible way to impact multiple health-related outcomes among older Veterans. Our Specific Aims reflect the primary outcomes that are the focus of the analyses, although we also will measure secondary outcomes related to VA healthcare utilization and patient safety:

**Specific Aim 1:** Implement a patient-centered deprescribing intervention (DROP) in the hospital to reduce the total number of medications Veterans are prescribed at hospital discharge.

**Hypothesis 1a:** DROP will result in a significant reduction in total medication exposure due to discontinuations and dose reductions at hospital discharge, SNF discharge and 90-days after SNF discharge.

**Hypothesis 1b:** DROP will result in a significant reduction in the number of potentially inappropriate medications (PIMs) at hospital discharge, SNF discharge and 90-days after SNF discharge.

**Hypothesis 1c:** DROP will result in a significant reduction in the anticholinergic and sedative drug burden at hospital discharge, SNF discharge and 90-days after SNF discharge.

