### Interventions to Deprescribe Medications and Knowledge Gaps

In recognition of the potential harms of polypharmacy, numerous studies have evaluated efforts to improve medication prescribing for older patients. Most interventions have applied the use of explicit criteria to reduce inappropriate prescribing with tools such as the Beers or STOPP, while a few considered other patient-centered factors (e.g., cost, convenience, life expectancy). Trials commonly use pharmacists, physicians or interdisciplinary teams to implement deprescribing protocols. However, there are several important gaps in knowledge, which this proposal will address. First, few interventions have been initiated in the hospital setting, and no deprescribing interventions have targeted older patients transitioning from acute to post-acute care, which may be an opportune time to deprescribe. The few trials that have been conducted have been disease-focused on deprescribing specific types of medications. Second, few trials have incorporated patient preferences into the decision-making process. A recent VA study implemented an electronic health record algorithm to identify medications for deprescribing; however, patients were not explicitly involved in the decision process. A recent qualitative study that included community-dwelling Veterans aged 65 and older with polypharmacy (mean = 13 medications/Veteran) demonstrated that most Veterans expressed a desire to take fewer medications. Finally, although most of the trials reported improvements in medication appropriateness, *there has been no study to evaluate the effects of deprescribing on health outcomes.*

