#### **Innovation:**

This trial is advancing science in multiple ways:

- 1) One of the first controlled intervention trials designed to improve post discharge outcomes for the high-risk population of older Veterans transitioning from hospital to SNF to home. Healthcare costs are increasing for this patient population, and they are at high risk for medication-associated complications and newly acquired geriatric syndromes.
- 2) Although the number of medications is strongly associated with increases in geriatric syndromes, it is unknown whether reducing medications will improve geriatric syndromes. This trial will generate data to evaluate the impact of medication reduction on Veteran health outcomes.
- 3) To date, there have been no controlled intervention trials focused on reducing the number of medications prescribed for hospitalized patients discharged to SNF, and the proposed intervention is one of the first to explicitly incorporate Veteran preferences into deprescribing efforts, which is consistent with Veteran-centered care initiatives. Moreover, our preliminary data show that incorporating patient preferences in the intervention protocol significantly changes these clinical decisions.
- 4) The proposed trial will evaluate both clinical effectiveness and implementation to inform the potential for DROP to be adopted into VA clinical practice.

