### **Secondary Outcomes – Geriatric Syndromes, Medication Adherence, and Functional Status**

Delirium: is assessed via the Brief Confusion Method (bCAM), a screening tool validated for use with hospitalized older adults. If the participant screens positive for delirium, no other participant interviews are conducted. Members of the research team will re-assess delirium daily during the remainder of the hospitalization; if/when the Veteran screens negative, the remaining assessments will be administered to the Veteran. If delirium persists throughout the hospitalization, the Veteran's surrogate is approached for syndrome assessments. The bCAM is not repeated at any other time point as it cannot be completed via telephone.

Cognitive Impairment: is assessed by the Brief Interview for Mental Status (BIMS), which has a total score range from 0 to 15 (0-7: severe impairment; 8-12 moderate impairment; 13-15 cognitively intact).

Depression: The Patient Health Questionnaire-9 (PHQ-9) is a validated screen to assess for depressive symptoms and their severity. Each item is scored from 0 ("not at all") to 3 ("nearly every day") to produce a cumulative score between 0 (no depressive symptoms) and 27 (severe depressive symptoms). If a Veteran reports severe depression or thoughts of self-harm, the study team elicits more information on their immediate safety then contacts the primary treatment team to close the loop for follow-up. The study team also offers to connect the Veteran with the VA's emergency helpline.

Urinary Incontinence: The International Consultation on Incontinence Questionnaire – Urinary Incontinence Short Form (ICIQ-UI SF) has four components and measures symptoms, frequency, and impact of urinary incontinence on quality of life. This tool has well established reliability and validity including sensitivity to treatment.

Unintentional Weight Loss and Poor Appetite: Nutritional concerns are assessed through the Determine Your Nutritional Health checklist, which is a 10-item tool utilized by the state government to determine nutritional risk in older adults receiving meal assistance. The checklist has 10-items which yields a nutritional risk score of 0-2 (low), 3-5 (moderate), and  $\geq 6$  (high). One item asks if they experienced a 10-pound weight change; if the Veteran indicates they had experienced a weight change, the study team will ask a structured question to clarify if the weight change was a gain or a loss.

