Pain: is assessed with the Brief Pain Inventory (BPI) short form, which has three primary components: location, pain severity, and pain interference with daily activities. The pain severity score is comprised of four questions (e.g., worst, best, average, current) in which the Veteran rates their pain on a 0-10 scale in the last 24 hours.

Falls: The Veteran (or their surrogate) is asked if they have fallen in the last month or since the previous timepoint during follow-up phase. If the response is 'yes,' then the patient is asked how many times they have fallen, and if any of the falls led to an emergency room visit or hospitalization.

Pressure Ulcers: At enrollment, the medical record is reviewed (via flowsheets and free text search) for the presence of pressure ulcers, including the staging (Stages 0-4). During the follow-up timepoints, the Veteran and/or their surrogate are interviewed directly about the presence of a pressure ulcer.

**Medication Adherence:** The Adherence to Refills and Medications Scale (ARMS) is 12 items on a Likert scale with the options ranging from “none of the time” to “all of the time.” Example questions include “How often do you forget to take your medicines?” and “How often do you put off refilling your medicines because they cost too much money?”. The assessment’s score range is 12 to 48 points with lower scores indicating better medication adherence.

**Functional Health Status:** The Vulnerable Elders Survey (VES-13) is a measure of health status that assesses a patient’s cognitive, physical and self-care activities, and self-rated health status. Scores range from 1 to 10, wherein lower scores indicate better health.

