**Hypothesis 2a:** Medication adherence will be measured using the ARMS based on an ordinal scale. Functional health status will be measured using the VES-13 total score, also an ordinal outcome. Patient attitudes toward deprescribing (PATD) also will be measured on an ordinal scale. The effects of intervention on these outcomes will be assessed at 7 (except PATD) and 90-days following SNF discharge using mixed-effects logistic regression or proportional odds logistic regression similar to analyses for Hypothesis 2b.

**Hypothesis 2b:** The prevalence and severity of geriatric syndromes will be analyzed at baseline, 7 and 90 days following SNF discharge. The effects of intervention on the prevalence of each type of geriatric syndrome will be assessed using mixed-effects logistic regression, adjusting for measurement time point (categorical) and its interaction with intervention. The severity of each geriatric syndrome is measured on an ordinal scale. Thus, severity will be analyzed using mixed-effects proportional odds logistic regression, also adjusting for measurement time point and its interaction with intervention. For either method random effects, testing, summary and diagnostic methods will be used as described for Hypotheses 1a, 1b and 1d.

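### The claim of more than 93% power at 260 Veterans covers all secondary outcomes but has no stated inputs, and it cannot hold for delirium at 7 and 90 days

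*Combined protocol and SAP*

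**What the plan says.** The Sample Size and Randomization section states: "It was determined that a sample of 260 Veterans was sufficient to provide power greater than 93% for both the primary and secondary outcomes". The same sentence appears in the Précis under Study Population and Sample Size. Neither place gives an effect, variance, alpha or evaluable number, or says whether 260 counts enrolled or evaluable Veterans. The original target was 540.

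Overview and Objectives describes power more narrowly: "The proposed randomized, controlled trial is powered to evaluate the effect of this intervention on a reduction in medications", followed by four medication measures. The next sentence reads: "In addition, we will collect relevant data on the prevalence and severity of geriatric syndromes and other clinical outcomes".

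The Study Design section makes geriatric syndromes, medication adherence and self-rated health the secondary outcome. Overview and Objectives instead attaches the word secondary to utilization and safety.

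The Schedule of Assessments lists delirium among the secondary geriatric syndromes, with N/A in the 7-day and 90-day columns. The description of the delirium assessment explains: "The bCAM is not repeated at any other time point as it cannot be completed via telephone". Hypothesis 2b nevertheless concerns prevalence and severity at 7 and 90 days, and its analysis says: "The effects of intervention on the prevalence of each type of geriatric syndrome will be assessed using mixed-effects logistic regression".

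On the size of effect to expect, the Innovation section says that "it is unknown whether reducing medications will improve geriatric syndromes", and the section on knowledge gaps says that "there has been no study to evaluate the effects of deprescribing on health outcomes". The hypotheses give a direction only.

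**The concern.** This sentence is the only statement in the documents that 260 is enough after the cut from 540. It covers every secondary outcome without qualification, and one of them has no measurement at the time points where it is to be tested. For the rest, a reader cannot find what effect the trial was sized to detect.

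Hypotheses 2a and 2b are formally tested at this size. With power above 93% on record, a non-significant result on syndromes, adherence or health status could be taken as evidence that deprescribing does not help. For some plausible effects the trial may have had little chance of showing a benefit.

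**Working it through.** **Reproducing the stated figure.** This is not possible, because no inputs are given. The check therefore runs backwards: what effect would give 93% power at this size?

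**Inputs.** From the plan: 260 Veterans, 1:1 allocation, so 130 per arm. Assumed: two-sided alpha 0.05 (the plan uses 95% intervals), no loss, no provider or SNF clustering. Syndrome prevalence is also assumed. Preliminary Data gives an average of 2.6 syndromes per Veteran; spread over the eight syndromes in the Schedule of Assessments this is 2.6/8 = 32.5%. No rate per syndrome is given, so 20%, 50% and 75% are shown too.

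**Delirium.** With no 7-day or 90-day value there is nothing to compare between arms at those times. Power under Hypothesis 2b is undefined, whatever the sample size.

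**Prevalence, single time point, unadjusted.** The required noncentrality is (1.960 + 1.476)² = 11.80. The detectable prevalence q from base p solves p − q = √{11.80 × [p(1−p) + q(1−q)] / n}. For p = 0.325 and q = 0.148, the right side is √(11.80 × 0.3455/130) = 0.177, which equals p − q.

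| Base prevalence | Needed at 130/arm | Needed at 94/arm |
|---|---|---|
| 20% | 6.0% | 4% |
| 32.5% | 14.8% | 12% |
| 50% | 29.6% | 26% |
| 75% | 55.1% | 52% |

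At 130 per arm the relative falls are about 70%, 54%, 41% and 27%.

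**Where 94 comes from.** If 260 means enrolled, the loss rates in Sample Size and Randomization (5% SNF deaths, 15% deaths by 90 days, 10% not reached) give 260 × 0.95 × 0.85 × 0.90 = 189, or about 94 per arm. Those rates were set for the original SNF-only population.

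**Effect of baseline adjustment and of using both calls.** Assume the same effect at both calls and within-person correlation ρ of 0.3 to 0.7. The variance is multiplied by 1−ρ² (one call, baseline-adjusted), (1+ρ)/2 (both calls), or (1+ρ)/2 − ρ² (both calls, baseline-adjusted). The two-degree-of-freedom test needs noncentrality 14.11. Including the single unadjusted test, the required level at 130 per arm becomes 6–10% from 20%, 15–20% from 32.5%, and 29–36% from 50%.

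**Scale scores (severity, ARMS, VES-13).** Single unadjusted test: √(2 × 11.80/130) = 0.43 SD. Both calls, baseline-adjusted, ρ = 0.7: √(2 × 14.11 × 0.36/130) = 0.28 SD. The range is about 0.28 to 0.43 SD. At 94 per arm the single unadjusted figure is √(2 × 11.80/94) = 0.50 SD.

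**Primary outcomes.** The same inputs are missing. The one usable SD, 5.3 for total medications at discharge, gives 0.426 × 5.3 = 2.26 medications at 130 per arm, unadjusted. This neither confirms nor refutes 93%, and it says nothing about PIMs or the drug burden index.

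**The original 540 chain (minor).** 540 × 0.95 = 513, as printed. Then 513 × 0.85 = 436, where the plan prints 393; and 436 × 0.90 = 392 (196 per group), where it prints 354 (177 per group). The printed values fit the 10% loss applied twice: 436 × 0.90 = 392, and 393 × 0.90 = 354.

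**The case against.** The strongest reply is that power is relative to an effect, and the plan states none, so the figure cannot be shown to be wrong. That stands for every secondary outcome that is measured at follow-up. Several stronger readings are tempting, and the documents do not support them.

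- **That all secondary outcomes need very large effects.** This fits prevalence at low or moderate base rates only. At 75% prevalence a 30% relative fall already has power of about 0.97 at 130 per arm, and scale scores need only a moderate effect.
- **That a one-fifth fall in a syndrome would usually be missed.** From 32.5%, power for that fall is 0.18 to 0.39 over the variants above. But the base rate is assumed, and a correlation of 0.8 with baseline adjustment and both calls raises it to about 0.51. It is an illustration, not a property of the trial.
- **That Overview and Objectives proves the syndromes are unpowered.** It names medication measures as powered but does not say only those, and it describes the trial as proposed, before the mid-study change. It is a mismatch to reconcile.
- **That delirium is measured only once.** It is reassessed daily in hospital after a positive screen. The gap is at 7 and 90 days, and the schedule shows it openly.
- **That pressure-ulcer severity has the same gap.** At follow-up "the Veteran and/or their surrogate are interviewed directly about the presence of a pressure ulcer", but the text does not say that stage goes unrecorded.
- **That limits on surrogate completion rule out a single N.** Evaluable numbers will differ by outcome, but one enrollment figure can be set to suffice for the smallest.

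The plan already summarizes effects with 95% confidence intervals, which reduces the risk of misreading a null result. It does not remove that risk while the power statement stands unqualified.

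**Conclusion.** The statement is wrong as written for delirium under Hypothesis 2b, and this needs no assumption. For the remaining secondary outcomes it is unsupported: no effect size appears anywhere, the plan itself calls the effect on syndromes unknown, and its two accounts of what the trial is powered for differ. It is also unclear which outcomes the word secondary covers.

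The size of the problem depends on assumed base rates, correlations and alpha. In the single unadjusted test without loss or clustering, prevalence must fall by roughly 14 to 20 percentage points from bases of 20% to 75%. Adjustment makes this smaller; loss to follow-up makes it larger. Scale scores need a moderate effect.

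A reader might infer that the 93% is sound for the primary outcomes. The documents do not establish that either, since the same inputs are absent. The arithmetic slip in the 540 chain is minor, errs on the conservative side and does not affect the 260.

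**What to change.** 1. In Sample Size and Randomization and in the Précis, limit the power statement to the outcomes for which it was calculated. For each, primary outcomes included, give the effect, the variance or base rate, alpha and the evaluable number. Exclude delirium at 7 and 90 days. Say whether 260 is enrolled or evaluable.
2. For secondary outcomes without such a calculation, remove the 93% claim and state the detectable effect at the expected evaluable number. Add to the analysis of Hypotheses 2a and 2b that results will be interpreted by the planned 95% confidence intervals, and that non-significance will not be reported as absence of effect.
3. Minor: correct the 540 chain to about 436 alive and about 392 reached (196 per group), or state the extra loss step behind the printed counts.

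The cost is text only, with no added enrollment, visits or procedures. The sponsor gives up an unqualified power claim for Aim 2.
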